| TITLE | The Effect of Chronic Pain on Delay Discounting in Methadone Patients |
|-------------------------|---|
| SPONSOR | D. [name] MHS |
| FUNDING | NIDA |
| ORGANIZATION | |
| NUMBER OF SITES | 1 |
| RATIONALE | The epidemic of opioid overdose deaths continues to rise, killing more persons in 2017 than HIV/AIDS at the height of that epidemic. Medication assisted treatment, including methadone and buprenorphine, is the standard of care for the treatment of OUD. However, chronic pain can reduce treatment efficacy during medication assisted treatment and is associated with illicit substance relapse, dropout, and subsequent overdose. Mechanisms by which chronic pain may influence the impulsive decision making (e.g., drug relapse) in persons with OUD have not been well characterized. A better understanding is needed of decision-making in this population. Two factors that can influence decisions to use drugs are impulsivity and acute opioid withdrawal. This proposal will test how chronic pain is associated with increases in impulsive decision making in OUD, whether impulsive decision making is greater when undergoing opioid withdrawal, and how catastrophizing may modify the association between withdrawal and impulsive decision making in patients with chronic pain and OUD. An ideal population for this developmental research project is methadone-maintained patients, who show high treatment attendance rates and will therefore assure study efficiency and reliable completion. |
| STUDY DESIGN | This proposal is a randomized double-blind placebo-controlled Phase 1 clinical trial / human laboratory study to assess the effect of acute opioid withdrawal precipitated by 0.1 mg IM naloxone on delay discounting in patients on MMT with and without chronic pain. |
| PRIMARY OBJECTIVE | Determine the effect of aversive stressors on delay discounting in persons in methadone maintenance. |
| SECONDARY OBJECTIVES | Investigate the degree to which trait pain catastrophizing modifies the association between opioid withdrawal and delay discounting in the PAIN group. Examine the effect of biological sex on discounting, opioid withdrawal, pain VAS, and pain catastrophizing Examine the association between somatization, depressive symptoms, anxiety and discounting. We expect to enroll 130 participants on MMT, 65 in the chronic pain |
| SUBJECTS | group (PAIN) and 65 in the group without chronic pain (NO PAIN). Assuming a 25% drop-out rate, we expect to have 50 completers of both experimental sessions in each group. |

| SUBJECT | Inclusion Cuitario |
|-----------------|---|
| SUBJECT | Inclusion Criteria: |
| SELECTION | 1) Male and female adults aged 18-65 |
| CRITERIA | 2) Stable methodone dose (at least 21 days) verified by |
| | contacting participant's opioid treatment program |
| | 3) Understand and speak English |
| | 4) Urine toxicology screen negative for drugs of abuse and |
| | positive for methadone |
| | 5) Must be without by signs of intoxication as evidenced by |
| | ability to receive full dose of methadone prior to research |
| | activities |
| | 6) Presence of chronic pain (>3 months) for the PAIN group and |
| | absence of pain for the NO PAIN group. |
| | Exclusion Criteria: |
| | 7) Unstable psychiatric illness as assessed by the Mini |
| | International Neuropsychiatric Interview (e.g. active suicidal |
| | ideation, psychosis) |
| | 8) Unstable medical illness as assessed by the study's |
| | independent medical monitor (e.g. uncontrolled hypertension, |
| | recent myocardial infarction, recent stroke, unstable angina) |
| | that may be affected by precipitated withdrawal |
| | 9) Prescription opioid use besides methadone |
| | 10) Acute pain process unrelated to chronic pain |
| | 11) Women who are pregnant or lactating |
| | 12) Known allergy to naloxone |
| | Patients will be allowed to re-screen if it is expected that an inclusion |
| | criterion not met or an exclusion criterion met will change prior to the |
| | end of study recruitment. |
| TEST PRODUCT | · |
| TEST PRODUCT, | Naloxone 0.1 mg IM |
| DOSE, AND ROUTE | Product will be administered once at the beginning of a study session. |
| OF | Administration will occur two hours after methadone dosing. |
| ADMINISTRATION | |
| CONTROL | Placebo injection (0.9% Normal Saline) |
| PRODUCT, DOSE | Product will be administered once at the beginning of a study session. |
| AND ROUTE OF | Administration will occur two hours after methadone dosing. |
| ADMINISTRATION | |
| DURATION OF | Subjects will be on study for an average of two to four weeks |
| SUBJECT | Screening: 3 hours |
| PARTICIPATION | Sessions: Each session will last approximately four hours. |
| AND DURATION OF | Sessions must occur at least 48 hours apart. |
| STUDY | |
| CONCOMMITANT | Beyond their methadone maintenance dose, participants will be |
| MEDICATIONS | allowed to take OTC or prescription strength non-opioid analgesic |
| | medications such as acetaminophen or ibuprofen for pain throughout |
| | the study, consistent with standards of care. |
| | Prohibited : Opioid analgesics other than methadone |
| | - I |

Version #: 1.9 Version Date: 12/09/2020 Page 6 of 37

| EVALUATIONS | | |
|-----------------------|--|--|
| PRIMARY ENDPOINT | Delay discounting of money rate (k) | |
| SECONDARY | Pain VAS ratings (0-100) | |
| ENDPOINTS | Peak COWS | |
| | Peak SOWS | |
| | Peak Change from Baseline Pupil Diameter | |
| | Peak VAS of Subjective drug effects (0-100) | |
| | Drug Effects | |
| | Good Effects | |
| | Bad Effects | |
| | Liking | |
| | • Sick | |
| OTHER | Pain Catastrophizing Scale | |
| EVALUATIONS | Barratt Impulsivity Scale-11 | |
| | Eysenck Impulsivity Questionnaire | |
| | Sensation Seeking Scale | |
| | Zimbardo Time Perspective Inventory | |
| SAFETY | Incidence of adverse events | |
| EVALUATIONS | Change in vital signs from baseline (HR, BP, RR, % oxygen) | |
| | saturation) | |
| PLANNED INTERIM | When approximately 10 patients have completed the study, an interim | |
| ANALYSES | analysis will be conducted by the study statistician. If there is no trend | |
| | of differences in delay discounting between placebo and naloxone | |
| | administration sessions, we would discuss with our NIDA program | |
| | official and independent medical monitor on the following two | |
| | options: increasing the dose of naloxone to 0.15 mg or administering | |
| | 0.1 mg naloxone at trough instead of peak methadone levels. Serious adverse events will be monitored by the medical monitor throughout | |
| | the duration of the study. | |
| STATISTICS | Using methods developed by co-I [name], nonlinear regression will | |
| Primary Analysis Plan | be used to calculate individual values of k, larger k values indicate | |
| Timary Analysis I lan | greater discounting or more impulsiveness. K values are normalized | |
| | using log transformation for parametric analysis. We will use repeated | |
| | measures analyses implemented in SAS PROC MIXED. The | |
| | dependent variable is k (discounting). Independent variables include | |
| | Group (PAIN vs. NO PAIN), a fixed, between-subjects effect and | |
| | Condition (control vs. withdrawal), a repeated, within-subjects effect. | |
| | The Group x Condition interaction will be examined to determine if | |
| | group differences vary by condition. Planned contrasts will explore | |
| | additive effects of chronic pain and withdrawal by examining whether | |
| | discounting by the PAIN group in the withdrawal condition is greater | |
| | than 1) discounting by the PAIN group in the control condition, or 2) | |
| | discounting by the NO PAIN group in the withdrawal condition. To | |
| | examine the effect of differing levels of peak aversive stimuli on | |
| | discounting, we will conduct analyses using only data from the | |
| | naloxone-precipitated withdrawal session that include peak COWS | |

Version #: 1.9 Version Date: 12/09/2020 Page 7 of 37

| | scores. |
|----------------------|---|
| Rationale for Number | Because there is no empirical data on within-subject changes in |
| of Subjects | discounting associated with naloxone precipitated withdrawal, we estimated change using data from a study by consortium PI [name] that used similar measures and found abstinence from smoking in nicotine-dependent individuals' decreased discounting rates ($f2$ =.02). For between group differences, we relied on data from our pilot study showing a correlation between pain and discounting (rho=.25) consistent with a small to medium effect size ($f2$ =.08). Three reported effect sizes for studies comparing opioid and tobacco dependent participants and non-dependent participants show much larger effects sizes (approximately $f2$ =0.4). Thus, basing the sample size on the effect size seen in the pilot study conservatively yields a sample size that will provide more than sufficient power to detect a group difference. Using these within-subject and between-subjects effect sizes, and assuming a correlation among repeated measures of 0.5, a final, analysis sample of 100 (50 per PAIN and NO PAIN groups) will provide greater than 80% power to detect significance (alpha=.05, 2-tailed) for between groups main effects, within-subject effects of condition, and the interaction between the two. |

Version #: 1.9 Version Date: 12/09/2020 Page 8 of 37

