3 STUDY OBJECTIVES

We hypothesize that the chronic pain group (PAIN) will show greater delay discounting (greater impulsivity) than the group without pain (NO PAIN) in both the control and opioid withdrawal sessions; and that discounting will be greater in the withdrawal session than control session for both groups, with the greatest discounting observed in the PAIN group while in withdrawal.

Version #: 1.9 Version Date: 12/09/2020 Page 11 of 37

We also hypothesize that across PAIN and NO PAIN groups, pain catastrophizing will independently modify the effect of precipitated opioid withdrawal on delay discounting, with higher levels of catastrophizing associated with a stronger association between withdrawal and delay discounting

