6 SUBJECT SELECTION

6.1 Study Population

The participants will be adult persons (age 18-65) with opioid use disorder who are currently maintained on a stable methadone maintenance dose. Half (50) of the completers will have chronic pain (PAIN group) and half will be pain free (NO PAIN group). Otherwise, the participants will be healthy enough (as determined by medical history, physical, and EKG) for study entry. Participants will be required to abstain from illicit substances and alcohol throughout the trial.

It is estimated that approximately 200 persons will have an in-person screening to enroll 130 participants on methadone maintenance that meet all inclusion/exclusion criteria. We will need 100 completers to have the necessary power to perform our statistical analysis, 50 persons in the PAIN group and 50 persons in the NO PAIN group.

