14.3 Analysis of Primary Endpoint

The primary hypotheses are that participants with chronic pain (PAIN) are more impulsive (larger k values) than participants without pain (NO PAIN) and that, within the same individual, k values will be larger in the naloxone-precipitated opioid withdrawal session compared to placebo. We will test these hypotheses using repeated measures analyses implemented in SAS PROC MIXED. The dependent variable is k (discounting). Independent variables include Group (PAIN vs. NO PAIN), a fixed, between-subjects effect and Condition (control vs. withdrawal), a repeated, within-subjects effect. The Group x Condition interaction will be examined to determine if group differences vary by condition. Planned contrasts will explore additive effects of chronic pain and withdrawal by examining whether discounting by the PAIN group in the withdrawal condition is greater than 1) discounting by the PAIN group in the control condition, or 2) discounting by the NO PAIN group in the withdrawal condition. To examine the effect of differing levels of peak aversive stimuli on discounting, we will conduct analyses using only data from the naloxone-precipitated withdrawal session that include peak COWS scores.

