14.6 Sample Size and Randomization

Because the within subject effect size of discounting changes associated with naloxone precipitated withdrawal are empirically unknown, an expected effect size of f^2 =.02 was assumed based on a study by [name] (consortium PI) showing that five days of cigarette smoking abstinence in nicotine-dependent individuals decreased discounting rates (93). This effect size was selected because it came from a study conducted by a study investigator showing a within-subject change in discounting for money, similar to the delay discounting outcome in the proposed study. The effect size for between subject differences in discounting between the PAIN and NO PAIN groups is expected to be f^2 =.08 for two reasons. First, the pilot data correlation between pain and discounting (rho=.25) suggests an effect size of small to medium magnitude by convention (110). Second, three previously reported effect sizes for studies comparing opioid and tobacco dependent participants to non-dependent participants (100) show larger effects sizes of approximately f^2 =.4. If between subject differences in the proposed study are of this larger magnitude, then sample size based on f^2 =.08 will provide more than sufficient power to detect a group difference in delay discounting rates.

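### The synopsis claims more than 80% power for the Group x Condition interaction without an interaction effect size; at 50 per group and correlation 0.5 that power needs a difference in change of about 0.57 SD

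*Combined protocol and SAP*

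**What the plan says.** The synopsis (Rationale for Number of Subjects) bases power on a final analysis sample of 100, 50 per group. It introduces the calculation with "Using these within-subject and between-subjects effect sizes, and assuming a correlation among repeated measures of 0.5" and concludes that there is "greater than 80% power to detect significance (alpha=.05, 2-tailed) for between groups main effects, within-subject effects of condition, and the interaction" of the two.

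Section 14.6 gives the source of the two sizes. For the within-subject effect, "an expected effect size of f^2 =.02 was assumed based on a study" of smoking abstinence. For the groups, "The effect size for between subject differences in discounting between the PAIN and NO PAIN groups is expected to be f^2 =.08". It gives no interaction effect size and no power figure.

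Section 3 hypothesises that "discounting will be greater in the withdrawal session than control session for both groups". Section 14.3 names two primary hypotheses, the Group effect and the Condition effect, and adds: "The Group x Condition interaction will be examined to determine if group differences vary by condition".

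On numbers, the synopsis enrols 65 per group and says: "Assuming a 25% drop-out rate, we expect to have 50 completers of both experimental sessions in each group". Section 14.1 likewise expects 100 completers. Section 6.1 says: "We will need 100 completers to have the necessary power to perform our statistical analysis". Section 12.2 rules out replacing participants who withdraw.

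**The concern.** A power figure means something only for a stated effect. Three effects are credited with more than 80% power, but only two have a size. A reader cannot tell what difference between the groups' responses to withdrawal the trial is meant to detect, or whether that difference fits the hypothesised pattern.

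What is at stake is how a non-significant interaction is read. A reader told that the test had more than 80% power may take it as evidence that the two groups respond alike. If both groups respond, as section 3 expects, the test may have had far less power than that.

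The completer forecast matters a little because Condition, which is a primary hypothesis, has no margin at 100.

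**Working it through.** **Inputs.** Two-sided alpha .05, correlation ρ = 0.5, N = 100 (50 per group), Condition f² = .02 and Group f² = .08 (synopsis and section 14.6). There are m = 2 sessions. The documents give no SD for log k, so effects are in SD units.

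**Reproducing the plan's figure.** Noncentral F with 1 and N − 2 degrees of freedom.

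- Condition: λ = N·m·f²/(1 − ρ) = 100 × 2 × .02/.5 = 8; power 79.97%.
- Group: λ = N·m·f²/(1 + ρ) = 100 × 2 × .08/1.5 = 10.67; power 89.9%.
- Interaction: same formula as Condition. It gives 79.97% if the Condition value f² = .02 is used for it.

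So the stated level reproduces to within rounding. An alternative convention, λ = N·f², gives only 29% for Condition, so it is not what the plan used.

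**What the interaction figure means.** With f = √.02 = 0.1414:

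- Average Condition change = 2f = 0.283 SD.
- Difference between the groups' changes = 4f = 0.566 SD.

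Cross-check by comparing change scores. The SD of change is √(2(1 − ρ)) = 1 SD. The noncentrality is 0.566/√(2/50) = 2.83, whose square is 8, as above. Hence 0.57 SD follows from 50 per group, ρ = 0.5 and 80% power, whatever f² convention is used.

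**Both values together.** PAIN = 0.283 + 0.283 = 0.566 SD; NO PAIN = 0.283 − 0.283 = 0.

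**If both groups change.** Let the NO PAIN change be a share r of the PAIN change and hold the average at 0.283 SD. The difference is then 2 × 0.283 × (1 − r)/(1 + r).

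| r | Difference (SD) | Interaction power |
|---|---|---|
| 0 | 0.566 | 80% |
| 10% | 0.463 | 63% |
| 25% | 0.339 | 39% |
| one third | 0.283 | 29% |
| one half | 0.189 | 15% |

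**Sensitivity to the correlation** (0.5 is the plan's value, the others are assumed; N = 100, average change 0.283 SD):

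| ρ | Difference detectable at 80% power (SD) | NO PAIN change it leaves (SD) | Power if r = one third |
|---|---|---|---|
| 0.4 | 0.62 | below 0 | 25% |
| 0.5 | 0.57 | 0 | 29% |
| 0.6 | 0.51 | 0.03 | 35% |
| 0.7 | 0.44 | 0.06 | 44% |
| 0.8 | 0.36 | 0.10 | 60% |

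**Sensitivity to the Condition effect** (assumed values, ρ = 0.5). The NO PAIN change left is 2√f² − 0.283: 0.03 SD at f² = .025, 0.06 SD at .03 and 0.12 SD at .04.

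**Completers.** 65 × 0.75 = 48.75 per group; 130 × 0.75 = 97.5 in total. At N = 97, Condition has λ = 7.76 and power 78.7%, Group power is 89.0%, and the detectable difference in change is 0.575 SD. Condition power first exceeds 80% at N = 101 (80.4%).

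**The case against.** The strongest reply is that the calculation reproduces. With two sessions the interaction is tested against within-subject error, so giving it the within-subject effect size is a natural reading. That stands: this is an unsupported power claim, not a calculation slip, and a reader who inferred an arithmetic error would be wrong.

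Second, a zero change in NO PAIN does not follow from 80% interaction power alone. It also needs the average Condition change to be 0.283 SD and the correlation to be 0.5. Section 14.6 admits that the within-subject effect is unknown and borrows its value, and the plan never sets out a joint scenario of cell means. That stands too, which is why the ranges are shown.

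Third, little depends on the interaction. It is not one of the two primary hypotheses in section 14.3. The section 3 pattern, with the greatest discounting in PAIN during withdrawal, can arise from two additive main effects. It would be tempting to infer that the trial is underpowered for its main questions, or that its hypothesis requires an interaction. The documents support neither.

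Fourth, the completer gap is 2.5%, and drop-out of 23.1% (30/130) would give exactly 100. A reader might infer that the power was computed on the wrong sample. It was not: the synopsis states it for 100. Only the forecast from enrolment falls short.

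What the reply does not supply is the interaction difference to which the claimed power refers.

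**Conclusion.** The point holds as a minor one. The claim of more than 80% interaction power has no stated effect behind it. At the plan's sample size and correlation it corresponds to a difference in change of about 0.57 SD. Taken with the planned average change, that leaves no room for the NO PAIN increase hypothesised in section 3. If both groups increase, with PAIN increasing more, interaction power on these inputs is below 80%, and it falls quickly as the two changes become more alike. This rests on ρ = 0.5 and Condition f² = .02 holding together; higher values of either relax it.

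Both main-effect powers reproduce at 100 completers, but Condition is at about 80%, not above it. The planned enrolment yields about 97 completers, which costs Condition 1.2 percentage points and Group 0.9.

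**What to change.** Wording only:

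1. In the synopsis rationale, take the interaction out of the power statement. Alternatively, say that 50 per group gives about 80% power for a difference of about 0.57 SD between the groups' changes at a correlation of 0.5, and that the interaction will be reported as an estimate with its 95% confidence interval. Carry the same text into section 14.6.
2. State Condition power as about 80% at 100 completers and about 79% at 97.
3. Correct the expected completers to 48–49 per group (about 97 in total) in the synopsis entry on subjects and in section 14.1. Leave 100 in the synopsis rationale and in section 6.1, where it is the design requirement, and note that the planned enrolment is expected to fall slightly short of it.

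The cost is a few sentences and two figures. Sample size, procedures and analysis model are unchanged; the stated power becomes slightly less favourable.

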1 BACKGROUND

1.1 Background/prevalence of research topic

Chronic pain is pain that has persisted for at least one month past the usual healing time of a specific injury, typically lasting for 6 months or longer (1, 2). Chronic pain is highly prevalent in persons with opioid use disorder (OUD), and is not sufficiently treated by opioid agonist treatment alone. Persons in methadone maintenance treatment (MMT) and office-based buprenorphine treatment for OUD have high rates of clinically significant chronic pain (37-80% depending on the definition) (3-6). Longitudinal studies have shown that chronic pain during MAT is associated with greater ongoing drug use (7-10), treatment drop out (9, 11) and risk of suicide (12) compared to patients without chronic pain. Together, these studies indicate that in MAT, pain is highly prevalent; MAT alone does not provide adequate analgesic relief; and ongoing pain contributes to worse treatment outcomes, including illicit substance use. Little is known about the behavioral/cognitive processes that may be affected by chronic pain, particularly processes associated with relapse while on MAT.

Delay discounting is the relative preference for smaller sooner over larger later rewards, an aspect of impulsivity. Most individuals would prefer an immediate \$100 over \$100 delayed by 1 year. However, when faced with the choice between receiving \$95 now versus \$100 in 1 year, preferences for the delayed reward may increase. By assessing such choices across multiple delays, delay discounting quantifies the devaluation of rewards over time, which allows for an index of overall discounting rate. Delay discounting models a fundamental decision in substance use disorders (SUD): the smaller immediate reward of drug euphoria, or the delayed but more valuable rewards of improved functioning and life satisfaction that come with prolonged abstinence (14, 15). The finding that individuals with SUD discount more than individuals without SUD has been shown for multiple drugs (16-21), including opioids (22-24). Effects are large and meaningful. For matched controls without OUD, \$1000 lost half its value in 5 years, while it lost 50% of its value in only 6 months for individuals with OUD: a 10-fold difference. Within patients with OUD, greater discounting is associated with increased sharing of injection equipment – an HIV risk factor. Studies in nicotine use disorder show that low delay-discounting predicts success in treatment (25-27), and one study showed a similar trend in MAT (p=.08) (28). Finally, recent research has suggested that aversive states, specifically opioid withdrawal, can further increase rates of discounting (29, 30).

Understanding the cognitive effect of aversive states (e.g. chronic pain) in patients with OUD could provide a potential for time-limited clinical interventions to prevent drug use. One of the seminal researchers in delay discounting (31) has proposed that the attention-focusing property of pain and other aversive stimuli is a result of delay discounting processes (32). Consistent with the hyperbolic bow in the shape of discounting curves (31, 33), pain is postulated to create strong immediate temptation to focus attention on the painful stimulus, at the expense of attention to other consequences, both immediate and delayed. From a cognitive perspective, immediate focus on pain likely leads to a reduced capacity to maintain attention and hold representations of potential future outcomes in

Version #: 1.9 Version Date: 12/09/2020 Page 9 of 37

working memory. Indeed, decreased attention and working memory load have been shown in chronic pain patients (34, 35). Little empirical research to date has explored the association between pain and discounting, although similar disruptions in central reward and executive control pathways in both patients with chronic pain and SUD provides strong theoretical basis for an association (36). Additionally, previous research has shown an increase in discounting associated with other aversive states including sleep deprivation (37), and importantly, opioid withdrawal (29, 30). In addition, our recent cross-sectional study showed a significant association between delay discounting of pain-specific consequences and risk for opioid misuse in chronic pain patients (38).

Another critical element in the experience of pain that increases attention to painful stimuli, catastrophizing (39, 40), provides an additional theoretical basis for the association between pain and discounting. Pain catastrophizing is a set of negative emotional/cognitive processes involving rumination and pessimism, perceptions of helplessness, and magnification of pain-related symptoms and is measured by the pain catastrophizing scale (PCS; (40)). Catastrophizing occurs during a painful experience or in anticipation of a painful experience. Research suggests that catastrophizing is directly associated with amplification of pain processing and is an etiologic/prognostic factor in several persistent pain syndromes (41-45). The tendency to and intensity of catastrophizing is relatively stable over time (40, 46, 47). Pain catastrophizing has been relatively unexplored in individuals with OUD, but recent clinical reports suggest catastrophizing may be an important psychological risk factor associated with opioid overdose fatalities (48, 49) and has been associated with craving and risk of opioid misuse in chronic pain patients at risk for OUD (50, 51). Given its importance and prognostic value in other chronic pain populations, this gap surrounding the role of catastrophizing in individuals with OUD and chronic pain needs to be filled. An ideal population to examine these associations are methodone-maintained patients, who show extremely high treatment attendance rates and will therefore assure study efficiency and reliable completion. Promising results would be followed up with an R01 application expanding the research, including extension to patients with OUD on buprenorphine and chronic pain patients on daily prescription opioid therapy without OUD but at risk for opioid misuse. By exploring mechanisms leading to impulsive relapse during aversive stimuli, this research may ultimately lead to targeted behavioral, cognitive, and/or pharmacological interventions that alter impulsivity and prevent relapse.

Provide a brief summary of the non-clinical data that has clinical significance.

